## Gene Therapy for Achromatopsia (CNGA3)

---

### 5.5.2 Secondary Outcomes

The secondary outcomes are measures of the efficacy of the ATIMP; these will be performed on an individual participant basis and will be descriptive in nature.

- Any improvements in visual function from baseline that are greater than the baseline variation and are sustained for at least two consecutive assessments.
- Any improvement in retinal function from pre – intervention that is greater than the baseline variation and measurable by electrophysiology (pattern ERG or full-field ERG). Quality of life will be measured by the Impact of Visual Impairment (IVI) questionnaire and the EQ5D-5L and EQ5D-Y, or equivalent as appropriate.

## 5.6 Trial Assessments

Table 2: Trial assessments

	Screening	Baseline 			ATIMP admin	D1	D3	W1	W2	W4	W6	W12	W24
Flexibility of schedule ( $\pm$ days)		- 9 months			Day 0	$\pm$ 0D	$\pm$ 1D	$\pm$ 2D	$\pm$ 4D	$\pm$ 7D	$\pm$ 7D	$\pm$ 14D	$\pm$ 14D
Visit number	1	2	3	4	5	6	7	8	9	10	11	12	13
Informed consent	•												
Physical exam	•												
Medical history	•												
Eligibility determination	•												
ATIMP administration					★								
Adverse event review		•	•	•	•	•	•	•	•	•	•	•	•
Concomitant medication review	•	•	•	•	•	•	•	•	•	•	•	•	•
Genetic screening 	•												
Pregnancy test	•				•								
Vital signs 	•	•				•		•	•	•			
Haematology 		•				•		•	•	•			
Biochemistry/glucose/liver and renal function 		•				•		•	•	•			
Serology		•								•		•	•
PCR						•				•			
QoL questionnaires (IVI and EQ5D-5L, or equivalent)		•											•
Visual acuity 	•	•	•	•		•	•	•	•	•	•	•	•
Colour vision assessments		•	•	•								•	•
Contrast sensitivity		•	•	•								•	•
Reading assessments		•	•	•								•	•
Static perimetry		•	•	•								•	•
Full Field Stimulus Testing		•	•	•								•	•
Ocular examination	•	•	•	•		•	•	•	•	•	•	•	•

**CNGA3CNGA3 Gene Therapy trial for Achromatopsia**

	Screening	Baseline 			ATIMP admin	D1	D3	W1	W2	W4	W6	W12	W24
Flexibility of schedule ( $\pm$ days)		- 9 months			Day 0	$\pm$ 0D	$\pm$ 1D	$\pm$ 2D	$\pm$ 4D	$\pm$ 7D	$\pm$ 7D	$\pm$ 14D	$\pm$ 14D
Fundus photography		•				•	•	•	•	•	•	•	•
Optical coherence tomography	•	•	•	•		•	•	•	•	•	•	•	•
Adaptive optics imaging		•	•										•
Fundus autofluorescence		•	•									•	•
Pattern Electroretinography 	•												•
Full field Electroretinography 	•												•
Photoaversion/ light sensitivity assessments (test and questionnaires)		• 	• 	• 								• 	• 

 Baseline assessments may be performed on the same day where considered logistically and clinically appropriate

 If result is available from prior testing, no repeat test mandated. Result will be reported into the CRF.

 Measurements for vital signs include: blood pressure, pulse, respiration rate, arterial oxygen saturation, temperature, height and weight

 Hematology to include the following parameters: Haemoglobin, Haematocrit, Erythrocytes, Mean Corpuscular Volume, Mean Corpuscular Haemoglobin, Platelet, Leukocytes, Absolute Neutrophils, Absolute Lymphocytes, Absolute Neutrophils, Absolute Eosinophils, Absolute Basophils

 Biochemistry to include the following parameters: Sodium, Potassium, Chloride, Bilirubin, Alkaline Phosphatase, Aspartate Aminotransferase, Alanine, Aminotransferase, Lactate Dehydrogenase, Gamma Glutamyl Transferase, Total Protein, Albumin, Calcium, Magnesium, Phosphate, Urea/BUN, Urate, Creatinine, Glucose

 Visual acuity at day 1 and 3 will be assessed using the previous refraction.

 ERG assessments may be performed under general anaesthesia if necessary.

 Photoaversion Questionnaire only to be completed at one baseline visit, "Photoaversion Device Questionnaire – Baseline" to be completed after every PA assessment

 "Photoaversion Device Questionnaire – after Surgery" to be used at week 12 and week 24 straight after Photoaversion assessments.

**For management of visits delayed due to COVID\_19 refer to appendix.**

## **CNGA3CNGA3 Gene Therapy trial for Achromatopsia**

---

### **5.6.1 Early Stopping of Follow-up**

If a participant chooses to discontinue their trial treatment, they should continue to be followed up as closely as possible to the follow-up schedule defined in the protocol, providing they are willing. If, however, the participant exercises the view that they no longer wish to be followed up either, this view must be respected, and the participant withdrawn entirely from the trial. MeiraGTX UK II Ltd. should be informed of the withdrawal. Data already collected will be kept and included in analyses according to the intention-to-treat principle for all participants who stop follow up early.

Participants who stop trial follow-up early may be replaced.

### **5.6.2 Loss to Follow-up**

This is a highly motivated patient group who are likely to remain committed to the research. Continued follow up of all participants will be strongly encouraged whilst being mindful of the importance of ensuring the autonomy of participants in regard to their treatment decisions and willingness to continue to participate in the trial.

### **5.6.3 Trial Closure**

The end of the entire trial is considered the last follow-up visit of the last participant. For each participant, the trial will terminate at the last scheduled visit 6 months following ATIMP administration. The MHRA and FDA will be notified of the end of the trial within 90 days of its completion.

### **5.6.4 Long Term Follow-Up After the End of the Trial**

At the end of this trial, participants will be invited to enrol in a follow-up study to determine the longer-term safety and efficacy up to 60 months' post treatment administration.

## **5.7 Sample Size**

This is a Phase I/II dose escalation trial to establish safety and assess indicators of potential efficacy of the ATIMP, therefore there is no formal sample size calculation. The trial will enrol up to 18 participants, as described in section 4.3.2.2. The limited number of participants is necessitated by the rare nature of the disease under investigation. The information obtained in this dose escalation study will help inform the design of a future Phase II interventional study.

## **5.8 Recruitment and Retention**

### **5.8.1 Recruitment**

Most participants will be recruited through Moorfields Eye Hospital, UK, or the Kellogg Eye Centre, US, or on referral by ophthalmologists within or outside the UK or US. Members of their direct clinical care team will approach potential participants in the first instance to discuss whether they would like to consider participating. Potential participants may also contact the trial team independently. We expect to recruit up to 18 participants in this dose escalation study.

### **5.8.2 Retention**

Participants will be supported to remain in follow-up by regular contact as per the protocol, provision of a 24-hour hotline to a member of the trial team.

## 5.9 Assignment of Intervention

### 5.9.1 Allocation

All participants will receive the same intervention in this open label, non-randomised trial: subretinal administration of AAV8-hG1.7p.coCNGA3 to one eye. The dose received by each participant will depend on the time/order of their enrolment in the trial according to the sequence of dose escalation, and the extent of dose limiting events (see sections 4.3.2 and 5.4.4 for dose escalation information).

## 5.10 Data Collection, Management and Analysis

### 5.10.1 Data collection, management and entry

Syne qua non will be responsible for data management activities for the study.

Data will be captured in a fully validated, 21 CFR Part 11 compliant Electronic Data Capture (EDC) system.

Authorised site staff with access to the EDC system following system training and a successful competency assessment.

Data required by the protocol will first be recorded on source documents (e.g. medical records and study-specific data capture tools as needed) and then entered by site staff into the EDC system. All information in EDC must be traceable to these source documents. Any data recorded directly into EDC will be defined prior to the start of data collection. All data is currently anticipated to be associated with source data records.

Data validation checks will be activated during data entry to identify data discrepancies. Appropriate error messages will be displayed to allow modification or verification of data by the site staff.

Monitoring staff will review the data for completeness and accuracy, instructing site staff to make any required corrections or additions via data queries. Data Management will run further automated validation checks and review the data, raising further data queries to the sites for resolution of any inconsistencies.

The Investigator will review the eCRFs for completeness and accuracy then electronically approve the data, retaining full responsibility for its accuracy and authenticity.

Medical history and adverse events will be coded using the Medical Dictionary for Regulatory Activities (MedDRA) terminology. Prior and concomitant medication will be coded using the World Health Organization Drug (WHO)-Drug Dictionary which employs the Anatomical Therapeutic Chemical (ATC) classification system.

Further coding details and data management processes will be described in a Data Management Plan (DMP).

All actions within the EDC system are captured within an audit trail. After all data, have been entered, validated and signed off, the database will be locked.

## **CNGA3/CNGA3 Gene Therapy trial for Achromatopsia**

At the end of the study, PDF copies of the eCRFs for each subject and supporting information will be provided to sites and the Sponsor. The electronic data will be provided to the Sponsor.

### **5.10.2 Non-Adherence and Non-Retention**

Participants who withdraw from the trial after the intervention will be encouraged to participate in any of the planned follow-up scheduled for the trial with their consent. Data collected prior to withdrawal will be considered in the interpretation of results.

Reasons for withdrawal from the trial will be documented on a withdrawal CRF where possible, in addition to the procedures and CRF for the final visit (6 month) assessments with the participant's consent.

### **5.10.3 Statistical Methods**

#### **5.10.3.1 Statistical Analysis Plan**

A formal Statistical Analysis Plan (SAP) will be approved by the sponsor. This trial is an open label, no crossover, phase I/II trial involving a small number of participants, and analysis of the primary and secondary outcomes will be descriptive in nature.

#### **5.10.3.2 Statistical Methods – Primary Outcome Analysis**

The primary outcome is safety of subretinal administration of the ATIMP defined as any of the below occurring during the 6 weeks following administration, at least possibly related to the ATIMP, not surgery alone:

- Reduction in visual acuity by 15 ETDRS letters or more that fails to resolve to within 15 letters of baseline in a 4-week period once prophylactic treatment commences
- Severe unresponsive inflammation
- Infective endophthalmitis
- Ocular malignancy
- Grade III or above non-ocular SUSAR (see section 5.11.3)

The number of DLEs at each dose level will be summarised by cohort and overall.

It is anticipated that the ATIMP will be administered at the MTD in up to 18 participants. Safety data relating to these participants will allow estimation of an upper bound for the true event rate through a 95% confidence interval.

#### **5.10.3.3 Statistical Methods – Secondary Outcome Analysis**

The secondary outcomes are measures of the efficacy of the ATIMP; these will be performed on an individual participant basis and will be primarily descriptive in nature. Standard assessments will be used to measure visual function and established methods of analysis, appropriate for the assessment will be used to evaluate the data. For specialist assessments, data will be analysed by the expert team member(s) who developed the assessment. Final data will be reported descriptively.

Efficacy will be indicated by:

- 1) Any improvement in visual function from baseline that is greater than the baseline variation for that test and is sustained for at least two consecutive assessments.

### **CNGA3CNGA3 Gene Therapy trial for Achromatopsia**

---

2) Any improvement in retinal function from pre – intervention assessment that is greater than baseline variation and measurable by electrophysiology (pattern ERG or full-field ERG).

Measures will be reported individually and aggregated across participants as the proportion who satisfy the above criteria.

Quality of life patient reported outcome measures will be used to correlate a participant’s feeling about their own wellbeing with clinical observations.

#### **5.10.3.4 Statistical Methods – Health Economics Analysis**

No health economic evaluation is planned, but the collection of EQ5D would allow Quality Adjusted Life Years (QALYs) to be calculated.

### **5.11 Data Monitoring**

#### **5.11.1 Safety Data Monitoring Committee**

To ensure the safety and efficacy and overall trial conduct, an SDMC will be established and take part in the data monitoring. The SDMC will consist of an independent consultant in pharmaceutical medicine who will be supported by the medical monitor, principal investigator and medical retina expert, and other independent uveitis or medical experts as required. The SDMC will make recommendations on the safety data prior to any dose changes.

Further details of the roles and responsibilities of the SDMC, including membership, decision making processes (and description of stopping rules and/or guidelines where applicable) are described in detail in the CNGA3 Gene Therapy Trial for Achromatopsia SDMC Charter.

#### **5.11.2 Interim Analyses**

No formal interim analysis is planned within the trial, but periodic reports concerning participant safety and key efficacy outcomes will be prepared for the SDMC as agreed in the SDMC charter.

#### **5.11.3 Data Monitoring for Harm**

##### **5.11.3.1 Safety reporting**

Pharmacovigilance services will be delegated to an appropriately qualified and evaluated service provider.

Definitions of harm of the EU Directive 2001/20/EC Article 2 based on the principles of ICH GCP apply to this trial.

**CNGA3CNGA3 Gene Therapy trial for Achromatopsia**

Table 3: Adverse Event Definitions

Adverse Event (AE)	Any untoward medical occurrence in a clinical trial participant administered a medicinal product and which does not necessarily have a causal relationship with this product.
Adverse Reaction (AR)	Any untoward and unintended response to an investigational medicinal product related to any dose administered This includes medication errors, uses outside of protocol (including misuse and abuse of product)
Unexpected Adverse Reaction (UAR)	An adverse reaction, the nature or severity of which is not consistent with the applicable product information (eg Investigator’s Brochure for an unauthorised product or summary of product characteristics (SPC) for an authorised product.
Serious Adverse Event (SAE) or Serious Adverse Reaction (SAR)	Any AE or AR that at any dose: 
 
• results in death
 
• is life threatening*
 
• requires hospitalisation or prolongs existing hospitalisation**
 
• results in persistent or significant disability or incapacity
 
• is a congenital anomaly or birth defect
 
• or is another important medical condition***
 

SUSAR	Suspected Unexpected Serious Adverse Reaction

* the term life threatening here refers to an event in which the participant is at risk of death at the time of the event; it does not refer to an event that might hypothetically cause death if it was more severe (e.g., a silent myocardial infarction)
 
** Hospitalisation is defined as an in-patient admission, regardless of length of stay, even if the hospitalisation is a precautionary measure for continued observation. Hospitalisation for pre-existing conditions (including elective procedures that have not worsened) do not constitute an SAE
 
*** Medical judgement should be exercised in deciding whether an AE or AR is serious in other situations. Important AEs or ARs that may not be immediately life threatening or result in death or hospitalisation but may seriously jeopardise the participant by requiring intervention to prevent one of the other outcomes listed in the table (e.g., a secondary malignancy, an allergic bronchospasm requiring intensive emergency treatment, seizures or blood dyscrasias that do not require hospitalisation, or development of drug dependency).
	

Adverse events include:

- an exacerbation of a pre-existing illness
- an increase in the frequency or intensity of a pre-existing episodic event or condition
- a condition (regardless of whether PRESENT prior to the start of the trial) that is DETECTED after trial drug administration. (This does not include pre-existing conditions recorded as such at baseline – as they are not detected after trial drug administration.)
- continuous persistent disease or a symptom present at baseline that worsens following ATIMP administration

## **CNGA3/CNGA3 Gene Therapy trial for Achromatopsia**

---

Adverse events do NOT include:

- Medical or surgical procedures: the condition that leads to the procedure is the adverse event
- Pre-existing disease or a condition present before ATIMP administration that does not worsen
- Hospitalisation where no untoward or unintended response has occurred e.g. elective cosmetic surgery
- Overdose of medication without signs or symptoms

### **5.11.3.2 Other Notifiable Adverse Events**

In order to manage the safety risks associated with administration of the ATIMP, all safety events will be reviewed within a short time frame for all participants, as described in the CNGA3 Gene Therapy Trial for Achromatopsia Data Management Plan.

Pregnancy is the only additional notifiable event that requires expedited reporting.

### **5.11.3.3 Procedures to follow in the event of female participants becoming pregnant**

A pregnancy test will be conducted for all females of childbearing age who are sexually active, and the results will be recorded in the medical notes before enrolling a volunteer to the trial. Females with a positive pregnancy test at this point will be excluded from the trial.

Where appropriate, a further pregnancy test will be performed on the day of administration of the ATIMP. Female participants with a positive pregnancy test at this point will be excluded from the trial prior to administration of the ATIMP.

Although participants are instructed to use double barrier contraception, we cannot exclude entirely that a participant might become pregnant after administration of the ATIMP. In the unlikely event that a participant is found to be pregnant we will notify their GP that she is participating in a gene therapy trial and that, although the risks involved are minimal, there is a chance of gene transfer to the unborn child. With the participant's consent, we will ask the GP/obstetrician to provide us with regular reports about the pregnancy until delivery. The pregnancy will be reported to the pharmacovigilance service provider on a pregnancy report form within 24 hours of the investigator becoming aware of the event. The participant will continue to be assessed until outcome of the pregnancy. However, if the participant is unable or unwilling to participate further in the trial, she will be encouraged to continue clinical monitoring visits to assess ocular health. In this situation, we may choose to enrol another participant to ensure the scientific validity of the trial.

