## 5.3 Participants

### 5.3.1 Eligibility Criteria

#### 5.3.1.1 Participant selection

The eligibility criteria for this trial have been carefully considered and are the standards used to ensure that only medically appropriate participants are entered. Participants not meeting the criteria should not be entered into the trial for their safety, and to ensure that the trial results can be appropriately used to make future treatment decisions for other people with similar diseases or conditions. It is therefore vital that exceptions are not made to these eligibility criteria.

Participants will be considered eligible for enrolment in this trial if they fulfil all the inclusion criteria and none of the exclusion criteria as defined below.

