#### 5.3.1.2 Participant Inclusion Criteria

Inclusion in the trial will be limited to individuals who:

1. Are aged 3-15 years
2. Have Achromatopsia confirmed by a retinal specialist (PI)
3. Have homozygous or compound heterozygous missense or null mutations in *CNGA3* confirmed in an accredited laboratory. Segregation is highly desirable but not essential if parental samples are not available.
4. Have evidence of relative photoreceptor preservation at the macula assessed by OCT +/- AO. Participants with normal ISe or minimally disrupted ISe on OCT will be prioritised.
5. Are able to give informed consent or assent, with or without the guidance of their parent/guardian where appropriate: children aged 3-6 years will not be required to provide assent
6. Are able to undertake age-appropriate clinical assessments at the trial sites as specified in the protocol
7. If female and of childbearing potential and sexually active, are willing to use an effective form of birth control (hormonal or double barrier method of birth control; or abstinence) for at least 12 months following ATIMP administration (Section 4.1.5, Assessment and Management of Risk)
8. If male and sexually active, are willing to use barrier and spermicide form of contraceptive or maintain sexual abstinence for at least 12 months following ATIMP administration
9. Females of childbearing potential will have a negative pregnancy test on the day of ATIMP administration. Participants are considered not of childbearing potential if they are pre-pubescent or surgically sterile (i.e. they have undergone a hysterectomy or bilateral oophorectomy)
10. Are willing to give consent for the use of blood and blood components collected throughout the trial for the investigation of immune responses to the ATIMP

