## Gene Therapy for Achromatopsia (*CNGA3*)

---

3. Physical examination
4. Vital signs including blood pressure
5. Ocular examination
6. Visual acuity
7. Spectral Domain Optical Coherence Tomography (SD-OCT)
8. Electrophysiological assessment

A letter from the general practitioner detailing the health status of the participant may be requested if the clinician deems it appropriate to confirm eligibility for the trial.

These assessments must have been completed within 9 months prior to enrolment. In addition, females of childbearing potential will undergo a pregnancy test at screening and again on the day of ATIMP administration.

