### 5.3.1.6.3 Enrolment

Participants who fulfil the inclusion criteria based on the results of all screening assessments and pregnancy test will be enrolled in the trial. The ATIMP will be administered within 9 months of enrolment. If the ATIMP is not delivered within 9 months of enrolment, all screening tests with the exception of genetic testing and electrophysiological assessment will be repeated and eligibility for enrolment re-assessed.

Participants who withdraw or are withdrawn from the study for any reason prior to ATIMP administration may be substituted in the study.

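### Protocol 5.11.3.3 narrows who has a pregnancy test and makes the dosing-day test conditional, in conflict with inclusion criterion 9, section 5.3.1.6.2 and Table 2; the contraception wording also differs

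*Protocol*

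**What the plan says.** Four places in the protocol deal with pregnancy testing before dosing.

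- **Inclusion criterion 9 (5.3.1.2):** "Females of childbearing potential will have a negative pregnancy test on the day of ATIMP administration". The group is then defined: "Participants are considered not of childbearing potential if they are pre-pubescent or surgically sterile". Sexual activity plays no part in that definition.
- **Screening Period (5.3.1.6.2):** "females of childbearing potential will undergo a pregnancy test at screening and again on the day of ATIMP administration".
- **Table 2 (5.6):** a pregnancy test is marked at screening and at ATIMP administration, with no limiting footnote.
- **Section 5.11.3.3:** before enrolment, "A pregnancy test will be conducted for all females of childbearing age who are sexually active". For dosing day, "Where appropriate, a further pregnancy test will be performed on the day of administration of the ATIMP". A positive result on either occasion excludes the participant.

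On contraception, criterion 7 covers sexually active females of childbearing potential and accepts hormonal methods, double barrier or abstinence. Criterion 8 covers sexually active males and asks for a barrier method with spermicide, or abstinence. Sections 5.11.3.3 (female participants) and 5.11.3.4 (partners of male participants) each say that participants are told to use double barrier.

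On the force of the criteria, 5.3.1.1 says: "It is therefore vital that exceptions are not made to these eligibility criteria". On timing, 5.3.1.6.3 says: "The ATIMP will be administered within 9 months of enrolment".

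**The concern.** Pregnancy is an exclusion criterion (5.3.1.3), and 5.11.3.3 itself acknowledges a possibility of gene transfer to an unborn child. The test is therefore the check that decides whether a female participant may receive the vector, and the protocol should give one rule for it.

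Instead, 5.11.3.3 states a narrower population and a softer dosing-day requirement than the eligibility and scheduling sections. Staff could reasonably turn to it at both points, because it says what is done before enrolment and on dosing day, and what follows a positive result. Its sexual-activity condition would ordinarily depend on disclosure, in a trial whose participants are mostly aged 3 to 15; the two US participants aged 18 or over could be affected as well.

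The conflict also blurs the record of conduct. SAP 5.5 lists all pregnancy test data. A missing dosing-day result would be a deviation under criterion 9, 5.3.1.6.2 and Table 2, yet could be read as allowed under 5.11.3.3.

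**Working it through.** The check is mainly a comparison of wording. The protocol gives no figure to reproduce.

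**1. Population and timing, side by side**

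| Place in protocol | Who | Pre-enrolment or screening test | Dosing-day test |
|---|---|---|---|
| Criterion 9 (5.3.1.2) | All females of childbearing potential | Not stated | Required, must be negative |
| 5.3.1.6.2 | All females of childbearing potential | Required | Required |
| Table 2 | No condition given | Scheduled | Scheduled |
| 5.11.3.3 | Childbearing age and sexually active | Required | Conditional, condition undefined |

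Criterion 9 states only the dosing-day test; the screening test comes from 5.3.1.6.2 and Table 2.

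**2. Is the difference in population only loose wording?** The inclusion criteria suggest not. Criterion 7 begins "If female and of childbearing potential and sexually active, are willing to use an effective form of birth control", so sexual activity is an added condition for contraception. Criterion 9, in the same list, leaves it out for testing. The protocol thus treats the two groups as distinct, and 5.11.3.3 applies the narrower one to testing.

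**3. What each reading means for a participant**

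- *Pre-pubescent or surgically sterile:* outside criterion 9 and 5.3.1.6.2, so no conflict arises between those two sections and 5.11.3.3.
- *Of childbearing potential and sexually active:* two tests under 5.3.1.6.2 and Table 2. Under 5.11.3.3 alone, one certain test and one conditional test.
- *Of childbearing potential, not recorded as sexually active:* two tests under 5.3.1.6.2 and Table 2. Under 5.11.3.3 alone, no required pre-enrolment test and no unconditional dosing-day test.

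**4. Age of a pre-enrolment result at dosing, if no dosing-day test is done**

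Age at dosing = (test to enrolment) + (enrolment to dosing).

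- Enrolment to dosing is at most 9 months (5.3.1.6.3).
- Test taken at about the time of enrolment: 0 + 9 = 9 months.
- If one assumes that the 9-month limit on screening assessments also covers the pregnancy test: 9 + 9 = 18 months.

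The second sum needs an assumption that the text does not settle. In 5.3.1.6.2 the 9-month limit follows a numbered list of eight assessments that does not include the pregnancy test, which is introduced afterwards as an addition. Section 5.3.1.6.3 also names the test separately from the screening assessments. Table 2 places it in the screening column, which leaves the matter open.

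**5. Contraception, by sex**

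- *Females:* double barrier (5.11.3.3) against hormonal, double barrier or abstinence (criterion 7).
- *Males:* double barrier (5.11.3.4) against barrier with spermicide, or abstinence (criterion 8).

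In neither case do the two statements match.

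**The case against.** The strongest reply is that the operative rules already agree. Criterion 9, 5.3.1.6.2 and Table 2 all place a test on dosing day, and 5.3.1.1 rules out exceptions to the eligibility criteria. Section 5.11.3.3 belongs to the safety-reporting part of the protocol and does not purport to waive a criterion. This stands to a large extent. A reader might infer that the plan permits a participant to be dosed untested; the documents do not support that. It would happen only if a site followed 5.11.3.3 in place of an inclusion criterion, the screening section and the visit schedule, and it would be a breach of criterion 9. That limits the consequence, but it does not remove the contradiction.

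A second reply is that the condition on the dosing-day test may simply mean those of childbearing potential. On that reading the dosing-day conflict disappears. The section does not say so, however, and the sexual-activity limit on the pre-enrolment test would still conflict with 5.3.1.6.2.

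A third reply is scale: the trial is small, the post-pubertal female subset is not quantified, and the SAP only lists the results. This stands, and is why the point concerns conduct and participant protection, not analysis.

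**Conclusion.** The inconsistency is real and lies in the current text. Section 5.11.3.3 disagrees with 5.3.1.6.2 on who is tested before enrolment. As worded, it also disagrees with criterion 9, 5.3.1.6.2 and Table 2 on whether the dosing-day test is unconditional. The contraception statements differ for each sex.

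The practical risk is that a site relying on 5.11.3.3 omits a test that the eligibility criteria require. Those exposed are females of childbearing potential: for both tests if not recorded as sexually active, for the dosing-day test otherwise. Their number cannot be derived from the documents.

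The documents support a pre-enrolment result up to 9 months old at dosing. A reader might add the two 9-month windows and conclude 18 months; that holds only if the screening window is assumed to cover the pregnancy test. The finding depends on neither figure.

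No endpoint, dose-escalation decision or statistical analysis changes. The point still merits correction, because it concerns a safeguard against fetal exposure that decides who may be dosed. No view is taken here on which testing or contraception rule is right.

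**What to change.** The sponsor should reconcile inclusion criteria 7 to 9 (5.3.1.2), 5.3.1.6.2, Table 2, 5.11.3.3 and 5.11.3.4 so that the protocol states throughout:

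- one population to be tested, described with one defined term;
- one set of test times, with any condition on the dosing-day test either defined or removed;
- one contraception instruction for females and one for males.

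When the test times are settled, the protocol should also say whether the 9-month screening window applies to the pregnancy test.

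The cost is a wording amendment. Both tests are already scheduled in Table 2, and the SAP listing of pregnancy test data needs no change.
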